### **Baseline**

Data will be collected on psychosocial factors (social support, quality of marital relationship, empowerment and functional disability, behavioral activation). We will also collect data on other socio-demographic variables including maternal age (years), maternal weight (kg), socio-economic assets (adapted from the Pakistan DHS), (44) marital status (married, single, widowed), education (years of formal education completed), and literacy (literate, semi-literate, not literate) and medically-related variables including gestational age of current pregnancy, number of pregnancies, history of SGA, LBW, PTB, stillbirth, and any complications in previous pregnancies/births. We will also collect data on current medications and current medical status, i.e. gestational diabetes, hypertension, anemia, mid-upper-arm circumference, smoking, substance abuse, and medication use for depression (though we expect these last three to be uncommon). An intimate partner violence (IPV) screening question will be administered so that referrals can be made if any women experience IPV. Women in the biological sub-study will also have their blood drawn (up to 20 mL) by a study clinician or a research assistant trained in phlebotomy. Each participant will be scheduled as close to possible to the same time of day during the morning hours for all four blood draws (as blood is drawn in HFH between 8:00am and 1:00 pm), allowing us to control for diurnal variation in cytokine levels. Blood will be collected in sodium-heparin tubes for immune cell preparation. Blood will be centrifuged within 8 hours of collection by low-density gradient centrifugation via a Z326 High Performance Centrifuge. Plasma will immediately be frozen in cryovials at -80 C in a ThermoScientific Revco RLE Ultra-Low Lab Freezer and will be stored there until it is shipped to Baltimore for analysis at the end of the trial.

### **At 24 weeks:**

Women participating in the biological substudy will have a blood draw (using same techniques described above under 'baseline visit') and will complete the HADS at this visit; other women in the main trial will not have a visit at 24 weeks.

### **At 3rd trimester**

Data will be collected about anxiety related to the pregnancy/delivery itself (PES-brief), perceived stress, fetal outcome (SGA in utero from medical records), social support, quality of marital relationships, functional disability and cost of service utilization and behavioral activation. An intimate partner violence (IPV) screening question will be administered so that referrals can be made if any women experience IPV. Women in the biological substudy will also have a blood draw (using same techniques described above under 'baseline visit').

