Pregnancy conditions: medical status in pregnancy (e.g. pre-eclampsia, gestational diabetes)	X			X	X	X
Adverse event review					AT ALL TIMES	

\*Baseline assessment may be the same day or up to two weeks after screening.

Note: Full descriptions of the assessment tools are given in section 8.2.3.

\*\*Assessments will be somewhat flexible; the 6-week postpartum visit can be done a week early and up to three weeks after the 6 week mark (if scheduling issues preclude collecting data exactly at the desired time)

§This screener will be administered in order to be able to refer women with IPV to counseling, since it is considered an adverse event.

§§Anthropometry will be measured either our team or a healthcare provider at the 6 week postpartum visit.

[figure not shown]
2. Describe the number and type of study visits and/or contacts between the study team and the participant, how long they will last, and where/how they will take place.

For the assessments there will be a screening visit at the time of enrollment, visit at baseline (either at the same time if the woman is ready to enrol or within 2 weeks afterwards if she would like more time to think about it), in late pregnancy, at delivery, and at 6 weeks postpartum. See above for assessments that will be done at each visit. We expect baseline and the 6 week postpartum visits to last between 1 to 1.5 hours. We expect the 3rd trimester visit to be shorter, around 45 minutes. We expect the birth visit to only entail 5 minutes of data collection with the women, while the rest will be gathered from medical records.

For women randomized to the intervention, there will be 6 core intervention sessions and up to 2-6 booster sessions (depending on the time of enrolment). The first five core sessions will be delivered weekly as early in the pregnancy as possible, then the booster sessions will occur, with one final core session (Core Session 6) in the 3rd trimester. Booster sessions will be scheduled on a case by case basis, depending on the recruitment time of the pregnant mother. Please see Table 2 above for an outline of session content.

For women in the biological substudy, there will be an additional visit at 24 weeks gestation for a blood draw and HADS administration. See the Figure below for a timeline of study visits.

Figure: Timeline for participants in the intervention and control arms of the main trial

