#### Analysis of Variables from Biological Substudy

**Statistical Analysis.** Oversight for the statistical analyses will be provided by [name] of the Johns Hopkins Biostatistics Center. The initial statistical approach will include a descriptive cross-sectional analysis at each time point, both for quality assurance and to attain a better understanding of the distributions of the outcome variables for use in subsequent analyses, including the need for any transformations, followed by the longitudinal analyses. For **Aim 1**, we will assess the associations between cytokine levels as dependent variables and level of anxiety (as measured by the HADS) as the independent variable. The level of anxiety will be considered from the following perspectives: 1) dichotomous (above and below HADS=8) and 2) continuous. In both analyses, we will compare women with anxiety vs. healthy controls and with and without the intervention to evaluate whether there is a positive association between

cytokines and other immune markers with anxiety. In addition, we will perform a comparison of immune markers between women disease/intervention groups adjusted for potential confounders that are differentially distributed by disease group, using multivariable linear regression model at each time point. We will assess whether association between immune marker and anxiety is different by group and by visit. In the longitudinal analyses, we will fit generalized linear mixed effect models to account for within-woman correlation of inflammatory markers. The model will include indicators for visit and group as well as any relevant interaction terms (e.g. group by visit). The models will adjust for baseline severity and other patient characteristics. A random effect for woman will be included as a random intercept. Other, more complex model structures will be explored, such as a model with random slope or non-independent residual correlation structure. These models account for missing at random, i.e. missing data are assumed to depend on prior immune marker values and covariates. Standard model checking will be performed and the most parsimonious model will be selected based on the Akaike Information Criterion (AIC).

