**Biological Outcome Variables:** Subjects will have their blood drawn (up to 20 ml) at all four visits by a study clinician or a research assistant trained in phlebotomy. Each participant will be scheduled as close to possible to the same time of day during the morning hours for all four blood draws (as blood is drawn in HFH between 8:00am and 1:00 pm), allowing us to control for diurnal variation in cytokine levels. Blood will be collected in sodium-heparin tubes for immune cell preparation. Blood will be centrifuged within 8 hours of collection by low-density gradient centrifugation via a Z326 High Performance Centrifuge. Plasma will immediately be frozen in cryovials at -80 C in a ThermoScientific Revco RLE Ultra-Low Lab Freezer and will be stored there until it is shipped to Baltimore for analysis at the end of the trial.

**Shipping of Samples:** Plasma samples (approximately 4800 cryovials) will be shipped from Pakistan to Baltimore at the end of the trial for analysis using Federal Express courier services. Blood will stay frozen at a minimum of -20 throughout shipment, using standard cold packs, dry ice, or liquid nitrogen as required by local regulations and the standards of the courier services. Because we will not be able to maintain a temperature of -80 during shipping, we plan to use multiple shipments (6-8) so that we can initiate analysis immediately upon arrival in Baltimore to avoid freeze-thaw cycles. (Shipping all vials at once will yield a batch too large for the capacity of our laboratory and staff to process at once.) Leftover samples will be refrozen for possible additional future analyses and will be stored in [name] lab at the Women's Mood Disorders Center, Johns Hopkins School of Medicine.

**Blood Sample timing:** Targets times for sampling blood will be at baseline (between 10 and 22 weeks), during the second trimester (24 weeks  $\pm$  2), the third trimester (36 weeks  $\pm$  2) and at 6 weeks  $\pm$  2 postpartum). All samples will be drawn in the morning (between 8:00 am and 1:00 pm) to minimize differences due to diurnal fluctuations in cytokine levels.

- If genetic/genomic analyses are planned, address whether the data will be contributed to a GWAS or other large dataset. Address returning unanticipated incidental genetic findings to study participants.

N/A

- If clinical or laboratory work will be performed at JHU/JHH, provide the JH Biosafety Registration Number.

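### No HADS is scheduled with the third-trimester substudy blood draw, so followed as written one of four planned HADS-marker pairs per woman is lost, and Table 4 needs reconciling with the text

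*Combined protocol and SAP*

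**What the plan says.** Section V, under Biological Outcome Variables, states that "Subjects will have their blood drawn (up to 20 ml) at all four visits by a study clinician". The Blood Sample timing paragraph begins "Targets times for sampling blood will be at baseline" and gives four targets: baseline (10 to 22 weeks), 24 weeks ± 2, 36 weeks ± 2, and 6 weeks ± 2 postpartum.

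The visit descriptions treat the two later pregnancy draws differently:

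- **At 24 weeks.** Substudy women have a draw and "will complete the HADS at this visit". The answer on number and type of visits repeats this: "there will be an additional visit at 24 weeks gestation for a blood draw and HADS administration".
- **At 3rd trimester.** The list opens "Data will be collected about anxiety related to the pregnancy/delivery itself (PES-brief), perceived stress" and continues with social support, marital relationship, disability, costs, behavioral activation and an IPV screen. It closes with "Women in the biological substudy will also have a blood draw". The HADS is not in the list.

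In Analysis of Variables from Biological Substudy, Aim 1 models markers with "level of anxiety (as measured by the HADS) as the independent variable", both split at 8 and continuous, and asks whether the association differs by group and by visit. Aim 2 follows the same approach with anxiety as the outcome, and models anxiety trajectories. Section I states Aim 2 as ALLO in pregnancy against concurrent anxiety symptoms and later postpartum depression.

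**The concern.** The HADS is the only anxiety scale that the substudy analysis names. If it is not given at the 36-week draw, that draw yields marker and ALLO values with no score on the scale the models use. Three things would be lost: the marker-by-HADS association at that visit, the HADS-ALLO pairing at the last pregnancy draw, and the late-pregnancy point of the HADS trajectory.

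The visit is informative. Women may enrol up to 22 weeks, and the first five core sessions are weekly. For a woman starting at 22 weeks, the fifth session falls at 26 weeks at the earliest (22 + 4), two weeks after the 24-week draw target. For such late enrollees, the 36-week draw is the only pregnancy draw planned clearly after those sessions. A score not taken then cannot be recovered later.

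**Working it through.** **1. The plan's own counts.** Section III.B allows 40% attrition: 180 / (1 − 0.40) = 300 enrolled, which agrees with the plan. The power statement there concerns group means of log cytokines. Those keep all four draws, so it is not the figure at issue.

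**2. Draws set against HADS administrations.**

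| Draw in the text | HADS in the visit text | HADS in Table 4 as read | Support elsewhere |
|---|---|---|---|
| Baseline | not named | marked | HADS at screening, at most two weeks before baseline |
| 24 weeks | named | marked | repeated in the answer on visits |
| 36 weeks | not named | blank | none |
| 6 weeks postpartum | not named | marked | HADS anxiety is a secondary outcome |

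Three of four draws have a HADS from some source. The third-trimester draw has none from any source.

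**3. How far Table 4 can be trusted.** Its blood-draw row, as read, is marked at screening, baseline, second trimester and 6 weeks, and is blank at the third trimester. That contradicts the text. Moving its first three marks one column to the right gives baseline, second trimester, third trimester and 6 weeks, which are the four draws in the text. The MSPSS, MRQ and WHO-DAS rows are marked for all women at screening and second trimester, although only substudy women have a 24-week visit. Apart from empowerment and behavioral activation, these are the kinds of measure the text places at baseline and third trimester. The HADS rows occupy the same columns as the blood-draw row, so the same shift would put a HADS at every draw. That is plausible but not proven, because a HADS at screening is also correct as the row stands.

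**4. Size if followed as written.**

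- Pairs per woman: 3 of 4, so 1/4 = 25% are missing; within pregnancy, 1 of 3.
- Among 180 completers: 180 × 4 = 720 planned and 180 × 3 = 540 obtained, so 180 are missing.
- At full enrolment: 300 × 4 = 1200 planned and 300 × 3 = 900 obtained, so at most 300 are missing.

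**5. What kind of loss this is.** As a gauge only, take the plan's exchangeable correlation of 0.6. The SD of a woman's mean over k measures, in units of the single-measure SD, is sqrt((1 + (k − 1) × 0.6) / k). This is sqrt(2.8/4) = 0.837 for k = 4 and sqrt(2.2/3) = 0.856 for k = 3, a rise of about 2%. An average over visits would lose little. What goes is the information specific to late pregnancy, which an analysis by visit and a trajectory both need. The gauge applies to means of repeated measures. The documents give no figure from which to compute the precision of a marker-HADS slope.

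**The case against.** The strongest reply is that the visit descriptions are not complete lists. The baseline and 6-week descriptions do not name the HADS either, yet it is plainly used at or near both. The 24-week paragraph may name it only because that visit exists solely for the substudy. With a table that looks shifted, a HADS at every draw may already be planned. This largely stands. A reader might infer that the visit text alone proves the omission, and it does not. What remains is that the other three draws have support elsewhere in the document and the third-trimester draw has none.

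A reader might also infer that no 36-week cross-sectional model can be fitted. The documents do not support that. The regression planned at each time point compares markers between disease and intervention groups, which are fixed at enrolment, so it needs no concurrent HADS. The mixed models with visit and group terms, and the powered comparison of cytokine means, also keep all four draws.

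It can be said that anxiety data do exist at the visit, since the PES-Brief and perceived stress are collected. That is true, so the gap is in the specified measure and not in all anxiety data. The PES-Brief cannot fill it across visits. It covers pregnancy-related anxiety, is assessed only at baseline and third trimester, has no stated equivalent of the cutoff of 8, and is nowhere named as a substitute.

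Finally, a reader might extend the point to the main trial. No planned main-trial analysis depends on a third-trimester HADS; the mediators named at that visit are stress, social support and empowerment.

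**Conclusion.** The point holds in a limited form. The protocol places a substudy draw at 36 weeks ± 2, schedules no HADS with it, and plans HADS-based analyses by visit and over time. If staff follow the document as written, 25% of planned HADS-marker pairs are missing by design (180 of 720 among 180 completers, and up to 300 of 1200 at enrolment). The missing-at-random statement in the substudy analysis concerns prior marker values and covariates, and does not address an anxiety score that was never scheduled.

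The count assumes that every completer gives all four draws, that the screening or baseline HADS serves the baseline draw, and that the 6-week HADS is given as Table 4 shows. It is a count of pairs, not a computed loss of power. HADS mixed models on three visits remain possible. If a third-trimester HADS was always intended, or is already being given, nothing is lost and only the documents need correcting. This affects a secondary study, but the remedy is cheap and the data cannot be recovered later.

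**What to change.** In At 3rd trimester, state that all substudy women, healthy controls included, complete the HADS on the day of the blood draw. Correct the HADS and blood-draw rows of Table 4 so that they match that section and the Blood Sample timing paragraph, and check the MSPSS, MRQ and WHO-DAS rows for the same shift. If third-trimester draws have already been done without the HADS, state in the substudy analysis that HADS-based models use three visits and that the by-visit association is not estimated at 36 weeks.

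The cost is a few minutes of each woman's time, with a questionnaire that staff already use at a visit already planned.

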### **At birth:**

Data will be collected on SGA, low birthweight and preterm birth. To evaluate IUGR at birth, we will classify small-for-gestational age (SGA) by using birthweight, gestational age, and sex of the infant, from the birth using the recently developed Intergrowth (45) standards (<http://www.intergrowth21.org.uk/>). Data will also be collected regarding

breastfeeding from mothers, and from the medical records regarding pregnancy outcomes and any medical conditions (e.g. pregnancy complications).

**Table 3: Birth outcomes and their definitions**

Endpoints	Measurement	Use and scoring
Intrauterine growth restriction (IUGR) at birth	At birth: Small-for-gestational age (SGA) will be used as a proxy for IUGR.	Use: Secondary outcome Scored: weight <10th% for gestational age
Preterm birth (PTB)	Weeks of gestation at birth	Use: secondary outcome Scored: <37 weeks' gestation
Low birthweight (LBW)	Weight in grams at birth	Use: secondary outcome Scored: ≤2500 grams

*\*We will also gather data from medical records on ultrasounds in the 2nd and 3rd trimester, in order to have the possibility of looking at fetal growth over time (measured then and at birth).*

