In our study, the unit of randomization is an individual woman, with an equal number of women randomized to the intervention and control groups. We assume an outcome prevalence of CMDs (postnatal depression episode and anxiety) at 30%, which is conservative given that most estimates of prenatal depression in Pakistan are higher than this. (16, 17, 91, 129) While we observed a 50% reduction in postnatal depressive symptoms when evaluating our prior CBT intervention (which was initiated late in pregnancy), we desire 85% power to detect reductions in CMDs as low as 30% (86, 130, 131), requiring 840 pregnant women (420 in each arm). Anticipating 30% attrition post enrollment, we will enroll 600 women per group in this study, for a total of 1200 women. This sample size of 420 outcomes per group provides ample power to detect important reductions in SGA, which we currently estimate to occur in approximately 47% of births. For example, we will have 90% and 80% power to detect reductions of 23.7% and 20.2%, respectively.

Sample size considerations for the qualitative process evaluation/COVID-questions will be based on a target number of up to 80 women sampled across different characteristics, or until saturation is achieved. We will sample up to 45 women from the intervention group and 25 women from the EUC group and another 10 who dropped out of the intervention. As described (See under Study Design above), these women will be purposively sampled to achieve a wide range of variation (or maximum variation) on various dimensions of interest. To triangulate and learn from multiple perspectives, we will also hold 2 focus group discussions (FGDs) with the HMHB therapists and assessors/screeners involved in delivery, assessments, or coordination of the intervention to ask them about their perspective on the same issues. Topics of interest for sub-group analyses include the effects of transitioning from in-person to by-phone format during the COVID pandemic, distress related to COVID-19, and the effects of prior miscarriage on current pregnancy and intervention experience.

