#### Analysis of Secondary Efficacy Endpoint(s)

We will secondarily compare the intervention and control groups in terms of changes in CMD symptom scores, by measuring depressive symptoms with the 9-item Patient Health questionnaire (PHQ-9) and the HADS anxiety questionnaires. Other outcomes of interest, but not primary targets, include birth outcomes (SGA, LBW, and preterm birth), perceived stress (using the Perceived Stress Scale –PSS), pregnancy-related anxiety (using the Pregnancy Experience Scale PES-Brief), maternal functioning (using WHO-DAS), marital relationships (MacArthur Relationship Questionnaire), IPV, women's empowerment, maternal bonding, maternal responsiveness, child growth at 6 weeks postpartum, as well as initiation and exclusivity of breastfeeding (WHO measures). Pregnancy-related symptoms of anxiety (measured with the PES-Brief) will be assessed at baseline and in the 3rd trimester.

For secondary hypotheses, we will estimate the effects of the intervention using birth and follow-up (6 weeks postpartum) measures separately. Primary analyses will be non-parametric tests, however sensitivity analyses will use parametric models such as linear and logistic regression to control for baseline values of the mothers' characteristics (132). Variable transformations (such as square root or log) will be utilized as appropriate to meet the model assumptions. For primary and secondary endpoints, in all regression models the coefficient on the HMHB vs. non-HMHB (control group) indicator variable will be taken as the estimated effect.

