## Moderator Analysis

To examine potential effect modifiers of the intervention treatment effects on birth outcomes, we will expand the regression models to include a term for the interaction between intervention group status and the potential moderators (exposure to social support, stress levels, marital relationship and empowerment measured at baseline as well as retrospective report of IPV measured at 6 weeks postpartum). This will allow us to examine whether the effects of HMHB differ for mothers (or their children) with varying levels of the potential moderators; analyses will be informed by recommendations in Aiken and West (1991)(140) and Preacher et al. (2006) (141). This aim will be exploratory given limited power for detecting interaction effects.

5. **Answer the following if they are relevant to your study design:**

- If the study has different arms, explain the process for assigning participants (intervention/control, case/control), including the sequence and timing of the assignment.

Study statistician will produce a random sequence of assignments to the study arms. This sequence will be generated using a pseudo random-number generator, and will be constructed using randomly permuted blocks of size 4, 8, 12, and 16. The assignment list will be printed in order, with each step of the sequence separately stored in opaque envelopes and numbered sequentially. When an individual who has been determined as eligible via the screening procedure subsequently provides consent for study participation, the X will pull the next available envelope, opening it, and recording the assignment to intervention or control.

In addition to the participants randomized through the main study, there will be three arms for the biological study. We will choose the first 100 participants each in the intervention and control arms, and will also recruit a group of 100 healthy controls (HADS <8) who will participate only in the biological study.

- If human biospecimens (blood, urine, saliva, etc.) will be collected, provide details about who will collect the specimen, the volume (ml) and frequency of collection, how the specimen will be used, stored, identified, and disposed of when the study is over. If specimens will be collected for use in future research (beyond this study), complete the "Biospecimen Repository" section below.
-

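### Fetal growth at birth is named only as yes/no outcomes (SGA, LBW); a prespecified birthweight z-score comparison could be added beside SGA from data already collected.

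*Combined protocol and SAP*

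**What the plan says.** Section V, "At birth", describes the derivation: "we will classify small-for-gestational age (SGA) by using birthweight, gestational age, and sex of the infant", using the INTERGROWTH standards. Table 3 turns this into a binary outcome, "Scored: weight <10th% for gestational age", as a proxy for intrauterine growth restriction. It scores LBW as a cut at 2500 g. The secondary-endpoint section lists these without any continuous counterpart: "Other outcomes of interest, but not primary targets, include birth outcomes (SGA, LBW, and preterm birth". For secondary outcomes it puts non-parametric tests first and mentions linear and logistic regression in general terms as sensitivity analyses.

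Section III.B bases its SGA power on a rate "which we currently estimate to occur in approximately 47% of births" and states "This sample size of 420 outcomes per group provides ample power to detect important reductions in SGA", giving the example that "we will have 90% and 80% power to detect reductions of 23.7% and 20.2%, respectively".

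Two items come near a continuous growth analysis. The Table 3 footnote keeps open the option of examining ultrasound growth over time, and the secondary list includes child growth at six weeks. Neither defines an analysis of size at birth.

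The Moderator Analysis section tests interactions on birth outcomes and says "This aim will be exploratory given limited power for detecting interaction effects". Aim 4 of the biological substudy examines mediation for preterm birth and SGA. The Missing Data section defers full detail to a statistical analysis plan to be finalised before unblinding. That plan is not among the documents.

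**The concern.** Better fetal growth is a main reason for starting treatment earlier than the previous third-trimester programme (section II), and SGA is a stated secondary objective. A yes/no cut discards how far each infant lies from the threshold. If treatment raises birthweight-for-age across the whole distribution, a comparison of SGA rates is more likely to miss it than a comparison of z-scores, and the trial could report no effect on growth where one exists. The interaction tests, which the plan already regards as weak, would lose power in the same way if they are run on the binary outcome.

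**Working it through.** **Inputs from section III.B:** 420 outcomes per arm, control SGA 47%, relative reductions of 20.2% and 23.7%, 1:1 allocation ("with an equal number of women randomized to the intervention and control groups").

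**Assumptions not in the documents:** two-sided 0.05 for the main trial (0.05 is stated only for the biological substudy); z-score normal with equal SD in both arms.

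**Step 1: reproduce the plan's figures.** The treated rates are 0.47 × (1 − 0.202) = 0.3751 and 0.47 × (1 − 0.237) = 0.3586. Power = Φ[(p1 − p2 − 1.96·SE0)/SE1], where SE0 = √(2·p̄(1 − p̄)/420) and SE1 = √([p1(1 − p1) + p2(1 − p2)]/420).

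- 20.2%: (0.0949 − 1.96 × 0.0341)/0.0339 = 0.83, power 79.6% (stated 80%).
- 23.7%: (0.1114 − 1.96 × 0.0340)/0.0338 = 1.33, power 90.7% (stated 90%).

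Both reproduce. With Fisher's exact test they are 77.5% and 89.6%.

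**Step 2: information kept by the cut.** Relative efficiency = φ(z)²/[p(1 − p)] at p = 0.47: 0.3978²/0.2491 = 0.64. At a 10% prevalence it would be 0.34, so a cut near the middle is the cheapest place to split a normal measure.

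**Step 3: z-score comparison under a uniform shift.** The shift giving the same fall in SGA is d = Φ⁻¹(0.47) − Φ⁻¹(p2). Power is Φ(d√210 − 1.96) for means and Φ(d√(210 × 3/π) − 1.96) for the Wilcoxon test.

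| SGA reduction | d (SD) | SGA | Wilcoxon | Means |
|---|---|---|---|---|
| 20.2% | 0.243 | 79.6% | 93.1% | 94.1% |
| 23.7% | 0.287 | 90.7% | 98.2% | 98.6% |

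The gain is 13.5 to 14.5 points in the first case and 7.5 to 8 in the second. At d = 0.243, 80% power needs 266 per arm for means and 424 for SGA.

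**Step 4: other patterns of benefit**, simulated at 420 per arm, all with the same fall in SGA (47% to 37.5%):

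| Who gains | SGA | Wilcoxon on z-score |
|---|---|---|
| Constant 0.243 SD, infants below the cut only | 80% | 39% |
| Constant 0.243 SD, up to 0.5 SD above the cut | 79–80% | 72–73% |
| Constant 0.243 SD, up to 1 SD above the cut | 80% | 89% |
| Larger gain in smaller infants, fading to zero at z = +0.5 to +2 | 78–81% | 82–88% |
| Steep gradient, fading to zero at z = 0 | 79% | 99% |

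**Step 5: illustrative moderator test.** Two equal halves (210 per cell), with the 20.2% reduction in one half and no effect in the other.

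- Binary: SE = √[(3 × 0.2491 + 0.2344)/210] = 0.0684; 0.0949/0.0684 − 1.96 = −0.57; power 28%.
- z-score, uniform shift in that half: SE = √(4/210) = 0.138; 0.243/0.138 − 1.96 = −0.20; power 42%.

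**The case against.** The strongest objection is that the gain is a product of the assumed shift. The plan wants to prevent poor growth and uses SGA as a proxy for growth restriction, which points to the lower tail rather than to larger babies overall. If small infants alone gain a constant amount, the z-score loses up to about 40 points. This stands. It rules out replacing SGA, and it rules out any single figure for the loss.

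A reader might infer that the plan throws away 13 power points. That figure belongs to the 20.2% case under a uniform normal shift; in the plan's other case the gain is about 8 points. A reader might also blame the position of the cut near the median, but Step 2 shows that this is the least costly place. Nor is the power statement in section III.B wrong: it reproduces, and it plainly refers to SGA prevalence.

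It is also fair to say that this is a brief plan in an ethics form, with detail deferred. The documents name no continuous analysis, but they do not exclude one. The moderator section does not say outright that its birth outcomes are binary; that is an inference from Table 3. Those tests are declared exploratory and stay underpowered even at 42%. Finally, no LBW rate is given, so no power claim is made for LBW.

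**Conclusion.** The point holds as a missed efficiency in secondary outcomes, not as an error. Size at birth is named only through binary cuts, while the data for a z-score are already collected. Under a uniform normal shift and a two-sided 0.05 level, both assumed, the z-score comparison is about 8 to 14 points more powerful at the plan's own two reductions. Under gradients that fade to zero between z = +0.5 and +2 the Wilcoxon gain is smaller, about 4 to 8 points. Under a constant gain confined to infants below or just above the cut, SGA is clearly better. The documents do not say which pattern to expect, so reporting both protects against either. They do not support making the z-score the lead fetal-growth outcome.

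**What to change.** Keep SGA and LBW as the named secondary outcomes. In the secondary-endpoint section, and in the statistical analysis plan due before unblinding, prespecify as a supporting fetal-growth analysis the difference between arms in INTERGROWTH birthweight z-score for gestational age and sex. Use a Wilcoxon test, with a linear-model estimate and 95% confidence interval. In the exploratory moderator analyses and the Aim 4 mediation analyses, report the z-score version alongside the SGA version. Section III.B needs no change.

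The cost is one derived variable and a few sentences, with no new visit, measurement or participant. The drawback is one more result in an already long secondary list, and a mean z-score difference is less directly clinical than SGA prevalence. Prespecifying it now matters because the same analysis added after unblinding would be post hoc.
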